Logistic regression and classification and regression trees (CART) will be used to develop a predictive model for successful management of early pregnancy failure, which will serve as the basis for a clinical predictive index [66-68]. Our group has used this methodology with success [69,70]. Initially the predictive model will only include biomarkers, and then both biomarkers and epidemiologic and clinical characteristics will be considered in the predictive model. The sensitivity of the predictive index (i.e., proportion of patients with success who are defined as “high chance of success” by the rule) will be of primary interest [71]. The negative predictive value will also be calculated using the derived sensitivity and specificity with the population prevalence of success. This value is also of clinical interest.

For model building, we will enter all biomarkers that will have shown in the bivariate analysis at least borderline associations with the endpoints of interest ($p < 0.20$), as well as interaction terms that are suggested by the results of the explanatory model. Terms will then be removed from the model using a backward elimination procedure, removing factors which cause an insignificant change in the sensitivity of the model. To test the change in sensitivity between models (with and without the variables), we will use McNemar’s test. In particular, we will be comparing the proportion of correctly classified cases of success between models. The rule would involve calculating a score for each person, based on the actual values of the regression coefficients. The goal is to utilize all variables that improve the sensitivity of the model. Unlike the explanatory model, whose goal is to determine which variables are associated with success, the predictive models will be developed in order to determine which combination of variables best predicts the outcome. Additionally, variables and interactions included in the model must be biologically plausible.

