7.4. Interim Analysis

Since safety and failure is a consideration in this study, we have chosen to use a group sequential design. Thus, in addition to the final analysis, we are planning on performing an interim statistical analysis during the course of the study. The purpose of the interim analyses will be to determine whether or not there is sufficient evidence of an increased failure rate in the combined arm compared to the control such that the trial should be discontinued prior to reaching the target accrual goal. The interim analysis will be performed after approximately 1/2 (150 subjects) of the total required patients have completed their primary outcome. This interim analysis will also examine whether or not there is sufficient evidence of an increased infection rate in the combined arm.

The primary outcome for the interim analyses will be the comparison of success/failure rates between the treatment arms. This comparison will be accomplished by means of a simple logistic regression model for the outcomes versus treatment. An approximate O’Brien-Fleming boundary will be used at the interim look to calculate the nominal significance level to which interim p-values are compared (O’Brien PC 1979). Using the O’Brien Fleming spending function, the two analyses (interim + final) should use the following incremental α values (0.003, 0.047) in order to achieve an overall $\alpha=0.05$.

Stopping criteria are for:

(1) **Clear superiority** -- whether the misoprostol alone is clearly inferior to combined treatment. For these calculations, we trade off the power to detect a difference and the size of that difference. Assuming $\alpha=0.003$ for boundaries for the interim analysis when 150 women have been followed to completion power is limited except to detect large reductions in failure rates. For example, power is approximately 0.80 to detect a reduction from 30% in the misoprostol alone arm to 6.7% in the

combination arm. Thus, early or premature stopping for superiority is unlikely, without dramatic improvement from the combined treatment.

(2) **Inferiority.** Power is limited to identify inferiority of the combined treatment, with 0.8 power to demonstrate a 30%-point increase in the risk of failure from 30% in the misoprostol alone arm to 60.7% in the combined treatment arm. Instead, we will base inferiority on the safety concern (see (4)) of an increased failure rate in the combination arm.

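### The McNemar rule for dropping terms from the logistic prediction model does not test whether a marker adds predictive information, and its error rates depend on a cut-off the plan does not state

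*Combined protocol and SAP*

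**What the plan says.** All of this is in section 7.2 (Statistical Methods) of the combined protocol and SAP.

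- Biomarkers enter the logistic model if their bivariate p-value is below 0.20. Backward elimination follows, "removing factors which cause an insignificant change in the sensitivity of the model".
- The criterion is explicit: "To test the change in sensitivity between models (with and without the variables), we will use McNemar’s test". It counts only women who succeeded, "comparing the proportion of correctly classified cases of success between models".
- The aim is also stated: "The goal is to utilize all variables that improve the sensitivity of the model". Sensitivity is the "proportion of patients with success who are defined as “high chance of success” by the rule".
- The section does not give, for this step, the predicted probability above which a woman is called a likely success, the significance level, whether a significant fall in sensitivity counts as a reason to keep a term, or whether specificity is held constant. It does not say that the comparison uses held-out data.
- Models are built for all women and then separately for each arm. CART is a second modelling route with its own entry screen (AUC above 0.6) and 10-fold cross-validation. CART and logistic rules are compared by ROC curves, and the prediction rule is validated by bootstrap.

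**The concern.** McNemar's test asks whether two classifiers fixed in advance are equally likely to gain or lose a correct classification. Here both classifiers are fitted to the women being classified, and one contains the other. The question that matters for selection is whether the marker's coefficient is zero given the other terms, and that is a different null hypothesis. A useful marker moves some successes above the threshold and others below it. These moves partly cancel, and all information on failures and on the size of the change in predicted probability is discarded. The plan then treats a non-significant result as grounds for removal.

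Sensitivity alone is also a poor guide, because a rule that calls every woman a likely success has 100% sensitivity. At stake is the secondary objective in section 2: which biomarkers, alone or combined with clinical characteristics, predict success. The selection step can lose real markers or keep useless ones, and a reader of the final score could not tell which had happened.

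**Working it through.** **The plan's own figure.** The plan gives no power or sample size for the biomarker model. The only related figure, 134 per group for 85% against 70% success (section 7.1), reproduces with a two-sided 0.05 test, continuity correction and 80% power (the power is assumed; 7.1 does not state it). It is not affected by this point.

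**Inputs from the plan.** 300 women, 150 per arm; success 85% and 70%. Pooled success is (85 + 70)/2 = 77.5%, so 0.775 × 300 gives about 232 successes and 68 failures.

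**Assumptions, because the plan gives no values.** Independent standard-normal markers; true OR 1.5 to 2.5 per SD; exact two-sided McNemar test at 0.05; cut-off varied over 0.5, the observed success rate, the Youden optimum, and fixed specificity of 60% or 80%.

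**The test.** Among observed successes, let b be those called likely successes only by the model with the marker, and c those called so only by the model without it. Then p = 2 × P(Bin(b + c, 0.5) ≤ min(b, c)). If every move is in one direction, five moves give 2 × 0.5⁵ = 0.0625 and six give 2 × 0.5⁶ = 0.031. So at least six successes must change category, nearly all the same way. The comparator is the likelihood-ratio test at 0.05.

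**Single removal step, N = 300, 77.5% success.** Share of runs in which the tested marker is kept. All rows except the Youden and 80%-specificity rows use two other markers at OR 1.6 and 2,000 runs per OR. The 80%-specificity row uses 600 runs per setting with differing numbers of other markers. The Youden row combines such 600-run results with a further three-marker simulation.

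| Rule | Useless (OR 1.0) | OR 1.5 | OR 2.0 |
|---|---|---|---|
| McNemar, cut-off 0.5 | 0% | 7% | 33% |
| McNemar, success rate | 2% | 9% | 31% |
| McNemar, 60% specificity | 18% | 43% | 75% |
| McNemar, 80% specificity | 21% | 49–51% | 67–77% |
| McNemar, Youden | 53–59% | 69–74% | 64–69% |
| Likelihood ratio | 5% | 79% | 99.6% |

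Varying the number of true markers from two to four puts the two fixed cut-offs at 5 to 36% over OR 1.5 to 2.0. At the Youden cut-off, retention hardly depends on whether the marker is useless or strong, so the rule barely discriminates there.

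**Loss against the likelihood-ratio test, from the 2,000-run results.** The largest is OR 1.8 at the success-rate cut-off: 0.980 − 0.208 = 77 points. The smallest is OR 2.5 at 60% specificity: 1.000 − 0.917 = 8 points.

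**Direction at cut-off 0.5.** With 77.5% success, a model without markers gives every woman a predicted probability of 0.775. All are called likely successes and sensitivity is already 100%. In the 2,000-run simulation every significant McNemar result at this cut-off was a fall in sensitivity when the true marker was added. Read literally, the rule keeps a marker because it lowers sensitivity. Read by the stated goal, it keeps none.

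**Full procedure, N = 300.** The p < 0.20 screen, then elimination, with three true and two useless markers; 200 runs per setting, Monte Carlo standard error about 3.5 points. Share of runs in which a true marker is kept:

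| Rule | OR 1.5 | OR 2.0 |
|---|---|---|
| McNemar, 0.5 | 5–8% | 20–30% |
| McNemar, success rate | 20–42% | 38–67% |
| McNemar, Youden | 57–68% | 60–68% |
| McNemar, 80% specificity | 42–55% | 73–84% |
| Likelihood ratio | 70–84% | 98–100% |

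At cut-off 0.5 the final model is empty in 56 to 87% of runs.

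**Per-arm model, N = 150, 70% success.** In the single step, retention of true markers is lower than at N = 300 at every cut-off. For example, with four markers at OR 2 it is 0.7% (0.5), 6.3% (success rate), 51.5% (Youden) and 43.7% (80% specificity), against 90.2% for the likelihood-ratio test.

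**The case against.** **The cut-off may be chosen sensibly.** The plan never proposes 0.5. It evaluates biomarker cut-offs by ROC curves and intends to optimise them. With a Youden or 80%-specificity cut-off, the full procedure keeps an OR 2 marker in 60 to 84% of runs. This stands. A reader might infer that the rule will usually discard the markers the trial is looking for; that holds at 0.5 and in most success-rate settings, but not generally. A better cut-off still does not repair the test, because the gain in retention comes with useless markers passing the single step far more than 5% of the time.

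**The entry screen limits the noise.** This also stands. After the p < 0.20 screen, the full procedure at N = 300 keeps a useless marker in 8 to 14% of runs at Youden and 4 to 9% at 80% specificity, against 4 to 8% with the likelihood-ratio test. The 20 to 60% figure belongs to the removal step alone.

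**The target is sensitivity, not association.** The plan separates its predictive model from its explanatory one, so a likelihood-ratio test measures something slightly different. Fair, but the rule also does badly on its own target. Counting a term as kept only when sensitivity significantly improves, full-procedure retention at N = 300 (OR 1.5 / OR 2) is 0% at 0.5, 4–8% / 10–16% at the success rate, 25–40% / 30–46% at Youden and 32–45% / 59–75% at 80% specificity.

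**CART and the single-marker summaries remain.** CART does not use this rule, and each biomarker's sensitivity, specificity and ROC curve are reported anyway. A reader might infer that the trial would conclude that markers do not help; the documents do not support that, because a marker dropped here can still appear by these routes. CART's screen is narrow for modest markers, though: a single normal marker at OR 1.5 per SD has AUC of about Φ(ln 1.5/√2) = Φ(0.287) = 0.61, just above 0.6.

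**Bootstrap validation.** It assesses the finished rule. It does not restore a dropped marker, and the plan does not say that selection is repeated in each sample.

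**Conclusion.** The concern holds in a limited form. The elimination rule is inefficient and does not test whether a marker adds predictive information. Whether it mainly drops true markers or lets useless ones through depends on a cut-off the plan does not state. In a single step at N = 300, with OR 1.5 to 2.0 per SD, it keeps a true marker about 7 to 33% of the time at a fixed cut-off and about 43 to 75% at a Youden or 60%-specificity cut-off, against 79 to 99% for a likelihood-ratio test. In every full-procedure setting examined it kept true markers less often than the likelihood-ratio test did. At cut-off 0.5 it works against the plan's own stated goal.

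No single miss rate can be quoted. Effect sizes, independence of markers, their number and the 0.05 level are all assumptions, and over OR 1.5 to 2.5 the single-step loss ran from about 8 to 77 points. It is also tempting to say that the arm-specific models always fare worse. The single-step results at 70% success show that, but the full procedure does not show it throughout: at cut-off 0.5 and OR 1.5, retention is 5 to 11% at N = 150 against 5 to 8% at N = 300.

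The consequence is confined to the logistic route of a secondary objective. The treatment comparison and its sample size are untouched. The change should be made, but the trial's main conclusion does not depend on it.

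**What to change.** In the model-building paragraph of section 7.2:

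1. Replace the McNemar removal rule with a likelihood-ratio or AIC criterion for each term, or with a penalised logistic model whose penalty is chosen by cross-validation.
2. Report sensitivity and specificity for the finished model at a cut-off that the plan states.
3. In the bootstrap paragraph, say that the whole selection, including the p < 0.20 screen, is repeated inside each bootstrap sample.

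In the same full-procedure simulation at N = 300, a likelihood-ratio criterion keeps a true marker in 70 to 84% of runs at OR 1.5 and 98 to 100% at OR 2. At N = 150 with 70% success the figures are 52 to 65% and 90 to 98%. Useless markers stay in 3 to 8% of runs.

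The cost is SAP wording and some computing time. No new data are needed, and the likelihood statistics come from models already being fitted. The downside is that the final score may keep a few more variables, which matters a little because the plan wants a rule that is easy to apply.

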The highly effective, safe combination regimen described above may also effectively treat women with EPF [11,12,39,58]. Our preliminary observations [11] strongly support this. However, this regimen needs to be rigorously tested in a sufficiently powered clinical trial [5]. The biologic basis for why a combination regimen should be more effective and safe than misoprostol alone, even in the cases of a failed pregnancy, has been preliminarily described. We and others have hypothesized that those failed pregnancies that do not respond to uterine evacuation with misoprostol alone appear to represent a subset of EPF in which the invasion of the extravillous trophoblast into the decidualized endometrium is altered [24,59]. This enhanced "attachment" of the pregnancy may be due to a direct trophoblastic effect, and/or may be due to characteristics of the decidualized endometrium. There is evidence for a direct supportive effect of P_4 on human trophoblast function [60], and therefore, this effect could be inhibited by the use of mifepristone. In addition, mifepristone also has anti-glucocorticoid activity, with relatively high binding affinity for the glucocorticoid receptor [20,21]. Since glucocorticoids are critical to

the function of human trophoblast cells [61], the presence of mifepristone could lead to decreased proliferation, differentiation, and/or invasive properties of the trophoblast – even in a failed pregnancy [62].

2 Study Objectives

Primary Objective

To compare the effectiveness of combination treatment (mifepristone premedication plus single-dose misoprostol) to single-dose misoprostol (standard of care) for the management of early pregnancy failure.

Our hypothesis states that the combination of mifepristone and single-dose misoprostol will be more effective than single-dose misoprostol alone, and will reduce the proportion of failed medical treatments (those who require repeat dosing or surgery) by at least 20% in 300 women seeking treatment for first trimester embryonic/fetal demise and anembryonic gestation.

Secondary Objective

[figure not shown]
To test the ability of trophoblastic and endometrial biomarkers to predict which women are most likely to succeed with medical management of early pregnancy failure and to derive and internally validate a prediction model designed to guide individualized counseling and treatment for early pregnancy failure.

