7.1. Sample Size Determination

Sample size calculations are based on detecting differences in the success rates between the misoprostol only and combined groups. Based upon prior research, we would expect a 60-71% single-dose success rate in the misoprostol only group [25]. Our preliminary data showed a 90% single-dose

success rate in the combined group using the proposed study regimen [11]. If we assume a conservative 85% success rate estimate for combined (C) and 70% success in the misoprostol only (M), we require 134 participants/group to show a difference if one is there (Table 2). To arrive at the total number of women needed to enroll, we inflate this estimate by 10% for loss to follow-up (5%) and interim analysis (5%). We will have adequate power to show a difference in success rates for all proportions above 10%. Thus, our proposed recruitment goal of 300 women (150/group) will enable us to find a clinically meaningful difference of 15% and confidently find the expected difference (20%) between groups.

Combination success rate	Misoprostol only success rate				
	50%	60%	65%	70%	75%
80%	n = 45 C: ±11.7% M: ±14.6%	n = 91 C: ±8.2% M: ±10.1%	n=151 C: ±6.4% M: ±7.6%	n = 313 C: ±4.4% M: ±5.1%	n = 1134 C: ±2.2% M: ±1.7%
85%	n = 33 C: ±12.2% M: ±17.1%	n = 57 C: ±9.3% M: ±12.7%	n=83 C: ±7.7% M: ±10.3%	n = 134 C: ±6.8% M: ±7.8%	n = 270 C: ±4.2% M: ±5.1%
90%	n = 25 C: ±11.8% M: ±19.6%	n = 38 C: ±9.5% M: ±15.6%	n=51 C: ±8.2% M: 13.1%	n = 72 C: ±6.9% M: ±10.6%	n = 113 C: ±5.5% M: ±8.0%
95%	n = 18 C: ±10.3% M: ±23.8%	n = 26 C: ±8.4% M: ±19.2%	n = 31 C: ±7.7% M: ±17.0%	n = 42 C: ±6.5% M: ±14.0%	n = 55 C: ±5.8% M: ±11.5%

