To be useful, a clinical rule must be easily applied. In order to ensure easy understanding and unhindered application, the variables and parameters comprising the predictive score will be simplified with two methods: 1) by recalculating the predictive score using values of the coefficients, rounded to the nearest integer, and 2) by calculating the score simply as the sum of the dichotomous independent variables identified by the model. (It will be necessary, for this approach to recode continuous predictors as dichotomous variables.) This will result in the most parsimonious model. The performance of the new rules will then be compared with that of more complete models using ROC curves. We plan to evaluate potential cutoffs of each marker to optimize our ability to distinguish among successes and failures.

We will also approach our predictive modeling using CART. Candidates that have an individual area under the curve (AUC) > 0.6 will be considered. CART is useful in identifying complex relationships between biomarkers and clinical outcomes. These analyses recursively split observations into two

groups (nodes), t_L and t_R , based on the covariate that maximizes a given split function. In the case of a continuous outcome, a commonly used split function is the reduction in sums of squares error, i.e. the amount of variability explained by the split. The best split is defined to be the one that best predicts the response where the best predictor is defined to be the one that maximizes the split function. All splits of the observations in each of the resulting nodes are then considered and the best split identified. This process is repeated recursively until a stopping rule is achieved (e.g. no further splits exist with greater than 5 observations in each of the resulting nodes). We will employ 10-fold cross-validation to assess the significance of the resulting tree as described in Breiman [72]. The sensitivity and specificity of the CART versus logistic model will be compared using ROC curves, to determine the best predictive rule for management success. CART software will be used to evaluate combinations of biomarkers creating a tree maximizing sensitivity and a tree maximizing specificity. Data will be combined into a three-tiered algorithm to maximize accuracy.

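### The predictive index uses unshrunk coefficients selected on the same women and no planned measure checks calibration, so any chance of success read from it is expected to be too extreme

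*Combined protocol and SAP*

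**What the plan says.** The secondary objective (section 2) is to derive and "internally validate a prediction model designed to guide individualized counseling and treatment for early pregnancy failure".

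Section 7.2 describes how the logistic index is built. Biomarkers enter if their bivariate association with the outcome has p<0.20, along with suggested interaction terms. Terms are then removed by backward elimination when McNemar's test shows no significant change in sensitivity. Clinical characteristics are considered after the biomarkers. On the weights it says: "The rule would involve calculating a score for each person, based on the actual values of the regression coefficients".

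Two simplified versions follow: coefficients rounded to integers, and a plain count of dichotomised variables. On these it says: "The performance of the new rules will then be compared with that of more complete models using ROC curves".

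Sensitivity is the measure of primary interest. NPV, specificity and ROC curves are also planned, 10-fold cross-validation is planned for the CART tree, and a bootstrap serves as internal validation. In the bootstrap, samples are drawn with replacement from the original data, predictive accuracy is tested in each, and the stated target is the test characteristics of the rule. Separate models per arm are planned, and differences between them are treated as groundwork for future research.

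Section 7.2 mentions no shrinkage or penalisation, no calibration slope, intercept or plot, and no repetition of the selection within the bootstrap.

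**The concern.** Coefficients that survive selection on the data used to fit them are, on average, too large. With few failures and many candidates, predictions spread too widely: too low for women ranked low, too high for women ranked high. Sensitivity, specificity, NPV and ROC curves depend on ranking or on a cut-off, so they do not respond to this spread.

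Counselling an individual woman about her chance of success depends on the size of that chance as well as on her rank. If the score is read as a probability, women in the lowest group would hear a chance that is too pessimistic, and the planned analyses would give no warning.

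**Working it through.** **1. Information available to the model.** Section 7.1 assumes success of 85% (combination) and 70% (misoprostol alone) and says "we require 134 participants/group to show a difference if one is there". With two-sided alpha 0.05 and 80% power (assumptions that reproduce the figure), the uncorrected size is

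n = [1.96·√(2·0.775·0.225) + 0.8416·√(0.70·0.30 + 0.85·0.15)]² / 0.15² = 120.5, so 121.

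The continuity correction, (n/4)·[1 + √(1 + 4/(n·0.15))]², gives 133.5, so 134, as stated. Inflating by 10% gives 148 (134 × 1.10) or 149 (134 / 0.90), consistent with 150 per group.

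Expected failures are 150 × 0.30 = 45 and 150 × 0.15 = 22.5, together 67.5.

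**2. Measure.** In new women, fit logit P(success) = a + b·LP, where LP is the linear predictor of the index. The calibration slope b is 1 when predictions have the right spread and below 1 when they are too extreme.

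**3. Simulation.** The documents do not give the number or strength of candidates, so these are assumptions: 5 to 30 candidates correlated 0.3, three of them real with log-OR 0.3 per SD (OR = e^0.3 = 1.35), screen at p<0.20, slope measured in 5,000 new women, 150 simulated trials per cell. Median slopes:

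| Candidates | 5 | 10 | 20 | 30 |
|---|---|---|---|---|
| All women, N=300 | 0.84 | 0.75 | 0.61 | 0.50 |
| Misoprostol arm, n=150 | 0.77 | 0.64 | 0.50 | 0.41 |
| Combination arm, n=150 | 0.67 | 0.55 | 0.44 | 0.33 |
| All women, strong markers (log-OR 0.6) | 0.93 | 0.85 | 0.68 | not run |
| All women, with McNemar elimination | 0.86 | 0.67 | 0.62 | not run |

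The last row assumes a cut at the observed prevalence and removal when McNemar p>0.05. It rests on 60 trials per cell and is noisy: with 10 candidates and 285 women the same procedure gave 0.84.

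In the pooled 20-candidate case (p<0.20 screen only), the lowest tenth was predicted 48% success and had 60%; the highest tenth was predicted 94% and had 90%.

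**4. Sensitivity to the set-up.** Runs with four real markers at OR 1.42 per SD gave pooled slopes of 0.63 to 0.75 with 12 candidates and 0.49 to 0.64 with 20, partly according to whether the OR is read as conditional or marginal. A further set gave 0.87, 0.76 and 0.63 for 5, 12 and 20 candidates. No scenario reached 1.

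**5. The bootstrap as described.** A maximum likelihood logistic fit has a calibration slope of exactly 1 in its own data. Testing that fixed rule in resamples of the same data therefore averages close to 1. The runs in step 3 gave means of 1.00 to 1.06, while the slope in new women was well below 1 in most of them.

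**6. A bootstrap that repeats the selection.** The p<0.20 screen and fit were repeated in each of 25 resamples per trial (50 trials per cell). Each rebuilt model was tested on the original women, and the index was multiplied by the mean slope. Median slopes in new women for 5, 10 and 20 candidates:

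| | Before | Estimated by bootstrap | After shrinkage |
|---|---|---|---|
| All women | 0.81, 0.71, 0.61 | 0.91, 0.82, 0.71 | 0.88, 0.86, 0.86 |
| Misoprostol arm | 0.80, 0.64, 0.49 | 0.84, 0.73, 0.59 | 0.93, 0.86, 0.78 |
| Combination arm | 0.67, 0.50, 0.41 | 0.79, 0.68, 0.52 | 0.89, 0.72, 0.76 |

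The problem becomes visible and is partly corrected. Across all sets of runs the pooled slope after shrinkage was about 0.84 to 0.97.

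**7. Integer rounding.** After shrinkage by 0.63, any raw coefficient below 0.5/0.63 = 0.79 rounds to zero. With 12 candidates and weights per SD, an all-zero score rose from 35% to 94% of trials in one run and from 37% to 67% in another. This depends on the marker scale.

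**The case against.** The strongest objection is that the plan nowhere converts the score into a probability for each woman. The stated outputs are a class of women with a high chance of success, an integer score, a count of dichotomised variables, CART trees and a three-tiered algorithm. A high or low class can also guide counselling. Multiplying all coefficients by one factor and resetting the intercept is a monotone change, so ranking, the ROC curve and classification at the matching cut-off stay the same. All of this stands: the point applies only where the score is used to state a chance of success.

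A reader might infer that the index is judged on sensitivity and ROC curves alone. The documents do not support that, since specificity, NPV, cross-validation of the tree and a bootstrap are also planned. What holds is narrower: none of them checks calibration. Predictive accuracy in the bootstrap is not defined further and could be stretched to include calibration, but the stated target is test characteristics, and step 5 shows that the described procedure would still miss the problem.

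The size is also open to challenge. The available text names only about five markers (activins, inhibins, glycodelin, βhCG, progesterone), and with five strong candidates the slope is a mild 0.93. Against that, section 1.2 refers to other markers, and clinical characteristics and interactions are candidates too, so five is a low end.

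**Conclusion.** The concern holds in a conditional form. The index uses unshrunk coefficients after two selection steps on the same women, and no planned measure would reveal miscalibration. If the score is used to state a woman's chance of success, the chances are expected to be too extreme. Over all pooled runs the slope was 0.81 to 0.93 with 5 candidates, 0.63 to 0.85 with 10 to 12, and 0.49 to 0.68 with 20; the upper ends come mainly from the strong-marker case. Slopes in the arm models are generally lower, because each has only 45 or 22 to 23 expected failures.

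The direction was the same in every scenario tried. The size rests on assumed numbers, strengths and correlations of markers that the documents do not give.

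A reader might go further and infer that women will be given wrong probabilities under this plan. The documents do not support that: no individual probability is an explicit output, and the arm models, where the error is largest, are described as groundwork for future research. This is a secondary aim, and the primary comparison is unaffected.

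**What to change.** - **List the candidates.** Name the biomarkers, clinical variables and interactions before the outcome data are examined, so that the expected size of the problem can be judged.
- **Amend the bootstrap paragraph of section 7.2.** Each bootstrap sample should repeat the whole process (p<0.20 screen, backward elimination, fit), and the resulting model should be tested on the original women. Report the optimism-corrected calibration slope and intercept, with a calibration plot, beside the ROC curve.
- **Amend the statement on score weights.** Wherever the score is given as a probability, use a penalised fit, or multiply the coefficients by the bootstrap slope and re-estimate the intercept. State that this corrects most but not all of the miscalibration.
- **Integer score.** Do not round shrunken coefficients directly. Rescale first, for example by dividing by the smallest retained coefficient (a common shrinkage factor cancels in that ratio), then round and recalibrate the score to observed risk.

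The cost is SAP wording and a modest extension of a bootstrap already planned, with no new data. The index will look less decisive.
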